## 16.2 Acronyms

AAA	Abdominal Aortic Aneurysm
ABI	Ankle-Brachial Index
ADE	Adverse Device Effect
AE	Adverse Event
CDT	Catheter-Directed Thrombolysis
CFA	Common Femoral Artery
CFR	Code of Federal Regulations
CIA	Common Iliac Artery
DSMB	Data and Safety Monitoring Board
DUS	Duplex Ultrasound
eCRFs	Electronic Case Report Forms
EC	Ethics Committee
EDC	Electronic Data Capture
EIA	External Iliac Artery
FDA	Food and Drug Administration
GCP	Good Clinical Practice
ICF	Informed Consent Form
IFU	Instructions for Use
IRB	Institution Review Board
ISO	International Standards Organization
ITT	Intent-To-Treat
LAR	Legally Authorized Representative
LE ALI	Lower Extremity Acute Limb Ischemia
LTFU	Lost to Follow-up
PAT	Percutaneous Aspiration Thrombectomy
PMT	Pharmacomechanical Thrombectomy
RHV	Rotating Hemostasis Valve
SAE	Serious Adverse Event
SFA	Superficial Femoral Artery
SOC	Standard of Care
SVS	Society for Vascular Surgery
TASC II	TransAtlantic Inter-Society Consensus for the Management of Peripheral Arterial Disease
TMF	Trial Master File
TIMI	Thrombolysis in Myocardial Infarction
UADE	Unanticipated Adverse Device Event
US	United States
VascuQoL-6	Vascular Quality of Life Questionnaire-6
XTRACT	Aspiration-Based Extraction Technique

## 17 APPENDIX II: Classifications and Scales

### 17.1 Rutherford Classification for Acute Limb Ischemia 

Category	Description / Prognosis	Findings		Doppler Signal	
		Sensory Loss	Muscle Weakness	Arterial	Venous
I. Viable	Not immediately threatened	None	None	Audible	Audible
IIa. Threatened Marginally	Salvageable if promptly treated	Minimal (toes) or none	None	(Often) Inaudible	Audible
IIb. Threatened Immediately	Salvageable with immediate revascularization	More than toes, associated rest pain	Mild, moderate	(Usually) Inaudible	Audible
III. Irreversible	Major tissue loss or permanent nerve damage inevitable	Profound, anesthetic	Profound, paralysis	Inaudible	Inaudible

### 17.2 Fontaine Classification 

Grade	Symptoms
Stage I	Asymptomatic, incomplete blood vessel obstruction
Stage II	Mild claudication pain in limb
Stage IIA	Claudication at a distance > 200m
Stage IIB	Claudication at a distance < 200m
Stage III	Rest pain, mostly in the feet
Stage IV	Necrosis and/or gangrene of the limb

### 17.3 Modified SVS Runoff Score 

Total Modified SVS Runoff Score is calculated from angiographic images. The score ranges from 1-19, with higher score indicating more severe disease. It is calculated by assessing the patency and degree of stenosis/occlusion in the popliteal artery and the three tibial vessels. The score for the popliteal artery multiplied by 3 and a value of 1 is added before adding all 4 vessel scores together.

Score (per vessel)	Level of disease
0	<20% stenosis
1	21-49% stenosis
2	50-99% stenosis
2.5	Vessel occluded over area < half its length
3	Occlusion > half the vessel length

### 17.4 TASC II Aortoiliac Lesion Classification 

Lesion Type	Description
Type A	Unilateral or bilateral stenosis of Common Iliac Artery (CIA) Unilateral or bilateral single short ( $\leq$ 3 cm) stenosis of External Iliac Artery (EIA)
Type B	Short ( $\leq$ 3 cm) stenosis of infrarenal aorta Unilateral CIA occlusion Single or multiple stenosis totaling 3-10 cm Involving the EIA not extending into the Common Femoral Artery (CFA) Unilateral EIA occlusion not involving the origins of internal iliac or CFA
Type C	Bilateral CIA occlusions Bilateral EIA stenoses 3-10 cm long not extending into the CFA Unilateral EIA stenosis extending into the CFA Unilateral EIA occlusion that involves the origins of internal iliac and/or CFA Heavily calcified unilateral EIA occlusion, with or without involvement of origins of internal iliac and/or CFA
Type D	Infrarenal aortoiliac occlusion Diffuse disease involving the aorta and both iliac arteries requiring treatment Diffuse multiple stenosis involving the unilateral CIA, EIA, and CFA Unilateral occlusions of both CIA and EIA Bilateral occlusion of EIA Iliac stenosis in patients with Abdominal Aortic Aneurysm (AAA) requiring treatment and not amenable to endograft Placement or other lesions requiring open aortic or iliac surgery

## 17.5 TASC II Femoral-Popliteal Lesion Classification 

Lesion Type	Description
Type A	Single stenosis $\leq$ 10 cm in length Single occlusion $\leq$ 5 cm in length
Type B	Multiple lesions (stenoses or occlusion), each $\leq$ 5 cm Single stenosis or occlusion $\leq$ 15 cm not involving the infrageniculate popliteal artery Single or multiple lesions in the absence of continuous tibial vessels to improved inflow for a distal bypass Heavily calcified occlusion $\leq$ 5 cm in length Single popliteal stenosis
Type C	Multiple stenoses or occlusions totaling $>$ 15 cm, with or without heavy calcifications Recurrent stenoses or occlusions that need treatment after two endovascular interventions
Type D	Chronic total occlusion of the CFA or Superficial Femoral Artery (SFA) ( $\leq$ 20 cm, involving the popliteal artery)

## 17.6 TIMI Flow 

Grade 0	No perfusion
Grade 1	Perfusion past initial occlusion but no distal branch filling.
Grade 2	Perfusion with incomplete or slow distal branch filling.
Grade 3	Full perfusion with filling of all distal branches.

17.7 Vascular Quality of Life – 6 

STATISTICAL ANALYSIS PLAN

STRIDE: A Study of Patients with Lower Extremity Acute
Limb Ischemia to Remove Thrombus with the Indigo®
Aspiration System

Protocol

CLP-15549

Version

26-Jan-2023

Contents

1	Overview	3
2	Study Objectives	3
3	Sample Size	4
4	Interim Analysis	5
5	General Statistical methods	5
6	Patient Disposition	5
6.1	Screened	5
6.2	Screen Failure	5
6.3	Enrolled	6
6.4	Completed	6
6.5	Early Termination	6
7	Definition of Analysis Population	6
8	Statistical Analysis	7
8.1	Primary Endpoint Analysis	7
8.2	Secondary Safety and Efficacy Endpoint Analysis	8
8.4	Handling of Multiplicity	9
8.5	Analysis of Deaths	9
8.6	Analysis of Adverse Events	9
9	Subgroup Analysis	10
10	Pooling Across Centers	10
11	Lost to Follow-up and Missing Data	11
12	Imaging Core Lab	11
13	Changes to Planned Analysis	11
14	References	12
15	Revision History	14
	Appendix A – Justification for Sample Size Calculation	16

1 Overview

This is a 12-month post-market, real world, prospective, single-arm, multi-center study to collect safety and performance data on the Indigo Aspiration System in a patient population with lower extremity acute limb ischemia (LE ALI).

Up to 130 patients presenting with LE ALI who are eligible for mechanical thrombectomy using the Indigo Aspiration System and who meet the inclusion, exclusion criteria will be enrolled at approximately 25 sites globally. Each site will be limited to a maximum enrollment of up to 26 patients (~20% of total enrollment).

Subjects will be in the study for approximately 12 months from enrollment to last follow-up. Follow-up assessments will occur at discharge and/or 7 Days whichever occurs first, 30 Day (\pm 14days), 180 Day (\pm 30days), and 365 Day (\pm 60days) following the procedure. Every follow-up treatment of patients will be recorded for the entire duration of the study. It is anticipated that enrollment will take approximately 24 months.

2 Study Objectives

The primary objective of interest is the target limb salvage rate at 30 Day post-procedure. The study limb salvage rate at 1-month (30 Day) post-procedure will be compared with the combined historical control rate of 95.7% observed under current standards of care.

The secondary objective of the study includes secondary performance and safety endpoints as detailed in the statistical analysis section below.

3 Sample Size

The sample size is calculated under the assumption of non-inferiority of the Indigo aspiration system in patients with LE ALI compared to current standards of care. The observed combined historical control rate of limb salvage is 95.7% under current standards of care (Appendix A). We assume that 94% (108/115) of the study subjects will achieve target limb salvage 1-month (30 Day) post-procedure.

Based on a binomial analysis with a non-inferiority margin of 10%, a study of 115 enrolled subjects will have approximately 80% power with a one-sided alpha of 0.025. The sample size was adjusted to 130 subjects to account for approximately 10% attrition.

Table 1:

Sample size calculation for Clinical Study with INDIGO Aspiration System in Acute Limb Ischemia CLP-15549.

Method	Normal Approximation
Number of Sides	Upper one-sided with alternative greater than null value
Null Proportion	0.957
Margin	-0.1
Alpha	0.025
Binomial Proportion	0.94
Sample Size	115
Variance Estimate	Null Variance
Computed Power	0.805

4 Interim Analysis

No interim analyses are planned for the purpose of terminating the study for a positive result. No adjustments will be made to the confidence bounds for the final analysis. Interim analysis may be performed for purpose of publication of study results.

5 General Statistical methods

Baseline data including, but not limited to demographics, clinical characteristics, and angiographic characteristics will be summarized using descriptive statistics. For categorical outcomes, the 95% two-sided confidence intervals will be calculated. For continuous outcomes, a 95% confidence bound for the mean or mean change from pre-procedure will be constructed. Results collected at multiple visits will be summarized at each visit, as necessary. Summaries for all measures will include all observed data for each visit. All analysis will be performed on the intent-to-treat population.

Analyses will be conducted using SAS© software Version 9.4 or higher (SAS Institute, Cary, NC).

6 Patient Disposition

The number of subjects for each of the following categories will be summarized for final analysis:

6.1 Screened

Screened subjects are all subjects considered for participation in the study, whether or not they sign informed consent.

6.2 Screen Failure

Screen failure subjects are all subjects considered for participation in the study, who failed to meet inclusion criteria or met exclusion criteria. Patients can be screen failed based on general criteria. These patients may or may not have signed an informed consent form.

6.3 Enrolled

An eligible patient is considered enrolled once informed consent is obtained and the Indigo Aspiration Catheter has been inserted into the patient's body.

6.4 Completed

Completed subjects are all subjects who were enrolled and completed the study follow-up or were known to have died prior to the last follow-up timepoint. The completed subject metric will be provided for 365 Day follow-up.

6.5 Early Termination

Early termination subjects are all subjects who were enrolled but did not complete follow-up and were not known to have died. The early termination subject metric will be provided for 365 Day follow-up.

7 Definition of Analysis Population

All performance and safety outcome measures will be analyzed under the intent-to-treat (ITT) principle. Under this principle, the ITT sample includes all subjects who are enrolled. This population is the primary analysis population.

A per-protocol (PP) sample is defined as a subset of the ITT sample. The per-protocol sample will include all subjects that do not have major protocol deviations (eg. eligibility violation or informed consent violations). In addition to the ITT, a per protocol analysis will be done for the primary and secondary endpoints.

8 Statistical Analysis

8.1 Primary Endpoint Analysis

The primary endpoint is a safety endpoint consisting of the target limb salvage rate at 1-month (30 Day) post-procedure. Limb is considered salvaged if no amputation was performed on target limb within 30 Day post procedure, or if target limb was amputated at or distal to the tarsal/metatarsal joint. The primary safety analysis will be the difference between the study group and the combined historical control rate of 95.7% observed under current standards of care.

The null hypothesis is that the difference between the primary endpoint rate and the standard of care at 30 Day post-procedure is less than or equal to -10%. The alternative hypothesis is the difference at 30 Day post-procedure is greater than -10%. Formally, the null and alternative hypotheses to be tested are as follows:

$$H_0: P_{\text{study}} - 0.957 \leq -0.10$$

$$H_A: P_{\text{study}} - 0.957 > -0.10$$

Where P_{study} is the proportion of patients who achieve target limb salvage 30 Day post-procedure.

The primary safety endpoint is met if the lower limit of the two-sided 95% normal approximated confidence interval of the primary endpoint rate is greater than 85.7%. The primary safety analysis will be unadjusted.

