## **10.8 Statistical Analysis of Primary Endpoint**

The primary endpoint is the target limb salvage rate at 1-month post-procedure. The primary safety analysis will be the difference between the study group and the combined historical control rate of 95.7% observed under current standards of care.

The null hypothesis is that the difference between the primary endpoint rate and the standard of care at 1-month post-procedure is less than or equal to -10%. The alternative hypothesis is the difference at 1-month post-procedure is greater than -10%. Formally, the null and alternative hypotheses to be tested are as follows:

$$H_0: P_{\text{study}} - 0.957 \leq -0.10$$

$$H_A: P_{\text{study}} - 0.957 > -0.10$$

Where  $P_{\text{study}}$  is the proportion of patients who achieve target limb salvage 1-month post-procedure.

The primary safety endpoint is met if the lower limit of the 95% confidence interval of the primary endpoint rate is greater than 85.7%. The primary safety analysis will be unadjusted.

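### The primary success rule uses a normal-approximation interval whose one-sided type I error is about 5% (3.4% to 6.0%, depending on the evaluable n), not the stated 2.5%, and it is not the test that was powered

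*SAP*

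**What the plan says.** SAP 8.1 tests H0: P − 0.957 ≤ −0.10, so the null boundary is 85.7%. It declares success if "the lower limit of the two-sided 95% normal approximated confidence interval of the primary endpoint rate is greater than 85.7" per cent. No formula is given. Protocol 10.8 sets the same threshold without naming an interval method: "The primary safety endpoint is met if the lower limit of the 95% confidence interval of the primary endpoint rate is greater than 85.7" per cent. The SAP is therefore the only text that fixes the method.

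SAP section 3 says that "a study of 115 enrolled subjects will have approximately 80% power with a one-sided alpha of 0.025". Table 1 in that section gives the method as "Normal Approximation", the variance estimate as "Null Variance" and the computed power as 0.805. Neither document checks the exact error rate of the success rule, or remarks that the power calculation and the analysis use different variances.

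**The concern.** A normal-approximation interval is ordinarily the estimate plus or minus 1.96 standard errors, with the standard error taken at the observed rate (the Wald interval). For a high proportion this standard error shrinks as the observed rate rises. Just where the decision is made, it is smaller than the standard error under the null, so the lower limit sits too high and the rule passes too easily. The powered test uses the null standard error and does not have this fault.

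Two things follow if this is right. The sample-size section and the decision rule describe different tests, so the stated alpha and power do not belong to the rule in force. And a device whose true limb-salvage rate is only 85.7% (14.3% limb loss) would be declared non-inferior more often than the plan says. This is the study's only primary test, so nothing else in the plan offsets the error.

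**Working it through.** **Inputs.** Historical rate 0.957 and margin 0.10 (SAP section 3), so p0 = 0.957 − 0.10 = 0.857. Assumed true rate p1 = 0.94, one-sided alpha 0.025 and n = 115 (SAP section 3 and Table 1). Enrolment of 130 with about 10% attrition leaves 130 × 0.9 = 117 evaluable.

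**Step 1: reproduce the plan's power.** With the null variance in the critical value,

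power = Φ[(p1 − p0 − 1.96·√(p0(1−p0)/n)) / √(p1(1−p1)/n)].

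At n = 115, √(0.857 × 0.143/115) = 0.03264 and √(0.94 × 0.06/115) = 0.02215. So power = Φ[(0.083 − 1.96 × 0.03264)/0.02215] = 0.805, as stated. With the observed-rate variance, as in a Wald interval, it is Φ(0.083/0.02215 − 1.96) = 0.963, which is not the stated figure. Table 1 therefore describes the null-variance (score) test only.

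**Step 2: compare the two tests on one result.** Take 105/115 = 0.9130, which is 0.0560 above 0.857.

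- Observed standard error: √(0.9130 × 0.0870/115) = 0.0263. The ratio is 0.0560/0.0263 = 2.13, above 1.96. The Wald lower limit is 0.9130 − 1.96 × 0.0263 = 0.8615, above 0.857: success.
- Null standard error: 0.03264. The ratio is 0.0560/0.03264 = 1.72, below 1.96. The Wilson lower limit is 0.847, below 0.857: no success.

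**Step 3: exact operating characteristics.** For each rule, find the smallest count x whose lower limit exceeds 0.857. The type I error is P(X ≥ x) for Binomial(n, 0.857), and the power is the same tail for Binomial(n, 0.94).

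| n | Rule | Successes needed | Type I error | Power at 0.94 |
|---|---|---|---|---|
| 115 | Wald | 105 | 0.0501 | 0.915 |
| 115 | Wilson score | 106 | 0.0256 | 0.847 |
| 115 | Clopper-Pearson | 107 | 0.0118 | 0.747 |
| 117 | Wald | 107 | 0.0433 | 0.907 |
| 117 | Wilson score or Clopper-Pearson | 108 | 0.0218 | 0.835 |
| 130 | Wald | 118 | 0.0577 | 0.951 |
| 130 | Wilson score or Clopper-Pearson | 120 | 0.0159 | 0.842 |

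**Step 4: is it an accident of one n?** Over all n from 115 to 130 the Wald error runs from 0.034 (n = 129) to 0.060 (n = 121), with mean 0.045, and is above 0.025 throughout. Over the same range the Wilson rule gives 0.013 to 0.026 and Clopper-Pearson 0.012 to 0.024.

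**Step 5: results whose verdict changes.** The results 105/115, 118/130 and 119/130 pass the Wald rule. Their Wilson lower limits are 0.847, 0.846 and 0.855, all below 0.857. Their exact one-sided p-values are 0.050, 0.058 and 0.032.

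**The case against.** The strongest reply is that Wald is a reading. SAP 8.1 gives no formula, and a score interval also rests on a normal approximation. If Wilson was meant, the type I error at n = 115 is 0.0256 and the inflation disappears. This is possible but not the ordinary meaning of the phrase, and nothing in the SAP says score. Even then the text would have to be made explicit, because the two readings give opposite verdicts on 105/115, 118/130 and 119/130.

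The second reply is that little turns on it. The rules differ by one success at 115 and two at 130. The planning result of 108/115 passes all three. At a true rate of 0.94 the chance that Wald and Wilson disagree is 0.915 − 0.847 = 0.068 at n = 115 and 0.951 − 0.842 = 0.109 at n = 130. The study is post-market and single-arm, and the Wald rule has ample power. All of this is true. But those one or two successes separate an error of about 5% from one near the stated 2.5%, the shift favours the device, and the plan itself chose a formal hypothesis with a stated alpha.

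Three narrower points stand. The factor of two is right at n = 115, but at 117 it is 0.0433/0.025 = 1.7, and it moves with the final n. Wilson is not strictly below 0.025 everywhere: it is 0.0256 at 115 and 0.0255 at 124. And Protocol 10.8 is silent on the method rather than wrong.

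**Conclusion.** The concern holds. With SAP 8.1 read as the Wald interval, the primary rule has an exact one-sided type I error of 0.050 at the planned n of 115 and 0.034 to 0.060 over n = 115 to 130, against a stated 0.025. The stated power of 0.805 belongs to a different test. The study is not underpowered as a result: exact power of the Wald rule is 0.89 to 0.95 over that range. The defect is that non-inferiority is too easy to declare when true limb salvage is at the 85.7% boundary. The figures treat the historical rate as fixed, as the SAP does, and take the evaluable number to lie between 115 and 130.

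**What to change.** In SAP 8.1, name the Wilson score interval in place of the normal-approximated one, and give its formula or the software option. It inverts the null-variance test that Table 1 already powers, so the sample-size section and the decision rule then agree. Have Protocol 10.8 refer to the SAP for the method. Restate the power as an exact figure for the interval chosen at the expected evaluable n: for Wilson, 0.847 at 115, 0.835 at 117 and 0.842 at 130.

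If control at or below 0.025 must be strict, use Clopper-Pearson instead. It gives the same cut-offs as Wilson at 117 and 130, but power falls to 0.747 at exactly 115 and 0.789 at 124, so the restated power should say so. With either interval, power is only 0.75 to 0.77 if the evaluable number falls to 112 to 114.

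The secondary proportions in SAP 8.2 have 95% intervals with no method named. Naming the same one there is sensible, since a Wald interval, if carried over, would have zero width for a zero count such as no device-related SAEs.

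The cost is a line of SAP text and a restated power figure, in a revised SAP of the kind that section 13 provides for. The Wilson change needs no extra patients; success needs one or two more salvaged limbs than under the present rule.

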8.4 Handling of Multiplicity

There will be no adjustment for multiple comparisons on the primary effectiveness variable since there is only one primary endpoint.

8.5 Analysis of Deaths

The Kaplan-Meier product-limit method will be utilized to assess the mortality rate. With the date of procedure set at Day 0, any death occurring on or before day 365 will be counted as a death. Patients who are alive past 365 days will be censored at 365 days. If clinical assessment is missing for a patient who has not died, the patient will be censored at the last follow-up date. The time to death will be plotted with confidence intervals.

Additionally, a cross-sectional analysis of mortality at 365 days will be performed. The frequency and proportion of deaths will be presented with the 95% confidence interval.

8.6 Analysis of Adverse Events

All adverse events, including serious adverse events (SAE), adverse device effect (ADE), and unanticipated adverse device effect (UADE) will be summarized by showing the number and percent of subjects which report the event. Events will also be reported by relationship to the procedure or device. Adverse events judged as probably or definitely related to the Indigo Aspiration System or procedure will be analyzed as device related or procedure related respectively.

Adverse events will be coded using the MedDRA dictionary. The number and percentage of subjects with AEs and SAEs will be summarized by body system and preferred term. Each subject will be counted only once within a category. An overall listing of each category will be provided.

9 Subgroup Analysis

To evaluate the association of baseline condition on outcomes, subgroup analyses will be performed for the primary efficacy variable (Target limb salvage at 30 Days), select secondary endpoints, patency at 30 Day (defined previously), and mortality at the 365 Day. The subgroups below will be assessed provided there are adequate sample size for analysis. Descriptive statistics will be presented for each subgroup with a 95% confidence interval for the difference between two groups.

- Thrombus and Lesion Location. The lesion location is the location of the underlying atherosclerotic disease.
 - Subjects with at least one thrombus located in the femoral-popliteal region (or proximal) vs subjects with tibial or distal vessel thrombus.
 - Subjects with at least one lesion located in the femoral-popliteal region (or proximal) vs subjects with tibial or distal vessel lesion.
- Severity of ALI at baseline (Rutherford classification IIA vs IIB)
- History of diabetes (Yes vs No)
- Index procedure in graft (Yes vs No)
- History of chronic limb ischemia (Yes vs No)

10 Pooling Across Centers

To assess the validity of data pooling, heterogeneity across sites and regions (North America vs Europe) will be examined using relevant methods, such as random effect models, ANOVA (continuous variables), contingency tables or binary logistic regression (categorical variables), GLM or Cox proportional hazards (event time variables) as appropriate. To avoid the influence of small enrolling sites on contingency tables, low enrolling sites will be removed as a sensitivity test for contingency table analyses.

11 Lost to Follow-up and Missing Data

